**Table 2. Digital Registry Schedule of Events**

Visit Windows	Baseline Visit	Weekly Activities	Monthly Activities from digital consent date up to 24 mos. post index PCI	Activities every 6 months from digital consent date
Informed Consent	x			
Eureka Registration	x			
Heart Rate	x (before and after the 6 minute walk test)	x (30 sec HR)	x (before and after the 6 minute walk test)	
Duke Activity Score	x		x	
Dyspnea Scale	x		x	
Angina Diary	x	x		
Seattle Angina Score	x		x	
6 minute walk test	x		x	
Geofencing (optional)**	x			
BORG Scale	x (after the 6 minute walk test)		x (after the 6 minute walk test)	
Medication Review **	x		x	
Hospitalization Review **	x		x	
Anxiety Survey	x			x

\*\*If additional information is required for patient entry visits, a member of the study team may reach out to the patient by phone to inquire about any ER visits, hospitalizations, or cardiac events.

Specifically, the digital registry activities are based on patient provided questionnaires such as: Seattle Angina Questionnaire, Duke Activity Status Index, Modified Medical Research Council Dyspnea Scale, and Anxiety survey: GAD-7. Other patient reported data collected may include the angina diary, hospital-geofencing, heart rate and activity measurements, and a self-performed 6-minute walk test. Hospital-geofencing refers to the ability of the Eureka application to identify if the subject has been within 200 meters of a hospital for 4 hours or longer. If so, a notification will be sent to patients inquiring about their symptoms, reason for hospitalization, and what specific tests were done (Figure 6). The 6 minute walk test is a self-performed test used in conjunction with the Eureka application. As part of the test, the application will measure the patient’s heart rate at rest, after test completion, and during recovery. The accelerometer function of the application measures the total distance walked in the allotted time, and also determines whether the patient has a change in cadence (pace), or takes time to rest. After the test, the subject will complete a Borg Rating of Perceived Exertion Scale survey which will include rating breathing difficulty at the worst part of the test and what if anything kept the subject from walking farther and faster.

The following disclaimer for participants will be included on the TAILOR-PCI digital follow-up website and informed consent form: The information obtained will be used solely for the purpose of research and will not be used to provide you with clinical care. If you experience any new or worsening symptoms, please contact your health care provider, or seek medical attention. If you think you are having a medical emergency, call 911.

To compare the accuracy of hospital-geofencing in discerning MACE, these subjects may also be contacted for follow-up by a study team member using a telephone script to determine whether MACEs have occurred. In the case that a hospitalization was not registered, the patient will be able to self-report any events as part of the follow-up phone notifications. If MACEs have occurred in subjects participating in the digital follow-up, Mayo Clinic Data Coordinating Center (MCDCC) will receive this indication in the file received from UCSF Eureka Data Coordinating Center (EDCC). If needed, a Mayo Clinic Digital Follow-Up study team member may obtain the subject's identifying information and Authorization to Release Protected Health Information from UCSF EDCC in order to request medical records from the patient's health care facility to ascertain clinical events. If MACEs are noted for subjects participating in the extended follow-up phone calls done by site study coordinators, medical records devoid of all patient identifiers will be sent to a designated study team member at the MCDCC to ascertain clinical events, as is being done in the parent TAILOR-PCI trial.

The consented subject in the digital follow-up may provide access to phone accelerometer-based step-counts and any self-report or connected device measures (such as weight or blood pressure) through HealthKit in iOS and GoogleFit in Android; may allow geolocation for determination when they are hospitalized; and may turn on notifications to allow the University of California San Francisco Eureka Data Coordinating Center to send push notifications for activities and surveys for hospitalization detection. Specifically, in addition to the consent, the participant will have to actively allow each of these as separate items (eg. share each HealthKit or GoogleFit item, turn on "share my location", and turn on "allow notifications"). In other words, they could opt out of any or all of these activities if they choose to do so.

#### **Patient Confidentiality:**

Patient-provided digital data will reside encrypted on the subject's phone until an internet connection is established, at which time the data is transmitted encrypted to the UCSF-Eureka data servers automatically. Once transfer is automatically confirmed via the endpoint (this happens as part of the built in API transferring data privately between the app and server), the data is deleted from the phone. The data servers are on a HIPAA-compliant stack in Amazon Web Services (BAA in place) and data is stored encrypted. The data being obtained is primarily patient-reported data. The transmitted data will be hosted on a HIPAA compliant cloud based platform provided by Amazon Web Services that is accessible to and managed by the University of California San Francisco Eureka Data Coordinating Center. This platform will generate a unique participant code tied to the TAILOR-PCI Subject ID that will also tie to the unique Eureka User ID created during registration. A Mayo Clinic Digital Follow-Up study team member may also access the subject's identifying information to request medical records from the patient's health care facility to ascertain clinical events. Follow-up study data from phone calls collected on TAILOR-PCI subjects is stored in the Medidata Rave system which is compliant with Code of Federal Regulations Title 21 (21 CFR) Part 11 and the Federal Information Security Management Act (FISMA). Both the physical and network security of the Medidata system is ensured through multiple measures. Physical security of the Medidata centers is managed through building guards, smart-ID badges with electronic access, video surveillance, and biometric scanners. Network security starts with border protection that includes routers and load balancers to provide high availability even during Distributed Denial of Service (DDOS) attacks. Data is protected from workstation to destination through the use of Secure Socket Layer (SSL) encryption with a minimum key length of 256 bits. The hosting site has dedicated disaster recovery facilities and automatically creates back-up files of the database on a regular basis according to standard research procedures. Each study site has access to only the data of subjects enrolled at their site. The site study coordinators will have edit access to the data and are responsible for entry and editing of all information obtained through follow-up phone calls. A Mayo Clinic Digital Follow-Up study team member will be responsible for entering digital enrollment in Medidata Rave, in addition to hospitalization and study endpoints obtained from medical records, if not already recorded by the site study coordinator. The Medidata web

interface will log users out of the application after extended periods of inactivity. Medidata Rave creates copies of the data formatted as SAS data sets on a server maintained by the Division of Biomedical Statistics and Informatics at Mayo Rochester on a nightly basis. These secondary files are only accessible by the Mayo statisticians and are controlled by UNIX group-access control. Login access to Division of BSI Unix workstations is secured by user-password controls. All study files stored on BSI servers are backed up nightly. All database and Web servers are secured by a firewall and through controlled physical access. All disk drives that provide network services, and all user computers, are protected using virus-scanning software.

Figure 4

[figure not shown]
[figure not shown]

Figure 5

Figure 6

## 12. OUTCOME DETERMINATIONS

### 12.1 Primary Outcome

The primary outcome will be the time to occurrence of the composite endpoint of a major adverse cardiac event (MACE), i.e. non-fatal myocardial infarction, non-fatal stroke, CV mortality, severe recurrent ischemia, and stent thrombosis if not captured in other events, from the time of randomization through one-year of follow-up.

### 12.2 Secondary and Exploratory Pre-specified Outcomes

Secondary outcomes will include: The incidence of major or minor bleeding in subjects with reduced function *CYP2C19* allele(s) receiving ticagrelor versus clopidogrel.

Exploratory pre-specified outcomes include:

- The effect of *CYP2C19*\*17 genotype on bleeding risk, MACE, stroke, and CV survival.
- The effect of *CYP2C19*\*2 or \*3 genotype on multiple recurrent events (MACE, stroke, and CV survival) in the individual subject.
- Performing a pharmacoeconomic analysis of the conventional therapy approach as compared with the genotype-based approach in subjects who undergo PCI.
- Comparing the occurrence of MACE in subjects with reduced function *CYP2C19* allele(s) to those with WT genotype receiving clopidogrel.
- Comparing the occurrence of MACE in subjects with reduced function *CYP2C19* allele(s) receiving ticagrelor to those with WT genotype receiving clopidogrel.
- Assessing the effect of CAD presentation: a) Stable coronary artery disease; b) Unstable angina or NSTEMI; and c) STEMI on the effect of ticagrelor in subjects with reduced function *CYP2C19* allele(s) and on the association of *CYP2C19* genotype and occurrence of MACE.
- To assess the mechanism of coronary stent thrombosis in subjects with reduced function *CYP2C19* allele(s) receiving ticagrelor versus clopidogrel.
- To assess implementation of a CLIA-approved *CYP2C19* pharmacogenetic testing on the

Spartan platform (accuracy of genetic testing by sequence analysis, and genotype failure rates).

- Exploratory outcomes will also include the individual components of the primary outcome.
- To assess compliance with dual anti-platelet therapy by phone survey.
- To assess patients' attitudes towards genotyping and the results of genotyping.

### 12.3 Clinical Event Definition and Adjudication

All clinical endpoints will be adjudicated by an independent Adjudication Committee that will be blinded to study treatment. The following clinical event definitions will be used by the Adjudication Committee:

#### Cardiovascular death

Death from cardiovascular causes or cerebrovascular causes and any death without another known cause.

#### Myocardial infarction

The diagnosis of myocardial infarction is dependent on whether it is *spontaneous*- or *procedure*- related:

- *Spontaneous*: Cardiac biomarkers (creatinine kinase-myocardial band, Troponin T or I) exceed the upper limit of normal according to the individual hospital's laboratory parameters or clinical presentation which is consistent or suggestive of ischemia.
- *Procedure-related excluding index PCI*:
  - In subjects with normal pre-procedural cardiac biomarkers, myocardial infarction within 24 hours post-PCI is indicated by cardiac biomarkers elevated above 3 times the upper limit of normal.
  - In subjects with elevated pre-procedural biomarkers, myocardial infarction within 24 hours post-PCI is indicated by cardiac biomarkers elevated above 3 times the upper limit of normal after biomarkers have exhibited a rise and fall indicative of completion of the presenting infarct.
  - MI greater than 24 hours post-PCI but prior to discharge is evidenced by any of the following:
    - a. A rise and fall in cardiac biomarkers (preferably troponin) with at least one of the values in the abnormal range for that laboratory, together with at least one of the developments listed below, is a manifestation of myocardial infarction. The abnormal range for your laboratory means levels above the 99th percentile of the upper reference limit (URL) for normal subjects.
      - i. Ischemic symptoms;
      - ii. ECG changes indicative of new ischemia (new ST-T changes, new left bundle branch block, or loss of R wave voltage);
      - iii. Development of pathological Q waves in 2 or more contiguous leads in the ECG (or equivalent findings for true posterior MI);
      - iv. Imaging evidence of new loss of viable myocardium or new regional wall motion abnormality;
      - v. Documentation in the medical record of the diagnosis of acute myocardial infarction based on the cardiac biomarker pattern in the absence of any items enumerated in 1-4 due to conditions that may mask their appearance (e.g. peri-operative infarct when the subject cannot report ischemic symptoms, baseline left bundle branch block, or ventricular pacing).
    - b. Imaging evidence of a region with new loss of viable myocardium at rest in

the absence of a non-ischemic cause. This can be manifested as:

- i. Echocardiographic, CT, MR, ventriculographic or nuclear imaging evidence of left ventricular thinning, or scarring and failure to contract appropriately (i.e. hypokinesis, akinesis, or dyskinesis);
  - ii. Fixed (non-reversible) perfusion defects on nuclear radioisotope imaging (e.g. MIBI, thallium).
- Peri-CABG (within the first 72 hours following CABG) is defined as an increase of biomarkers greater than 5 times the upper limit of normal for your laboratory (i.e. above 5 times the 99th percentile upper reference limit for a 'normal' population) compared with the pre-CABG biomarker value closest to the time of surgery plus one of the following:
    - New pathological Q waves or new LBBB;
    - Angiographically documented new occlusion or thrombosis of a graft or native coronary artery since the preoperative angiogram;
    - Imaging evidence of new loss of viable myocardium at rest in the absence of a non-ischemic cause.

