### **Severe recurrent cardiac ischemia**

Recurrent cardiac ischemia and at least one of the following, but not fulfilling the criteria for MI:

- New or presumed new ischemic ECG changes (ST elevation  $\geq 1$  mm (0.1 mV) or ST depression  $\geq 0.5$  mm (0.05 mV), or T wave inversion  $\geq 1$  mm (0.1 mV) in at least 2 adjacent leads)
- Leading to urgent revascularization (PCI or CABG) unless not advised on reasoned grounds. Urgent revascularization (PCI or CABG) must occur during the same hospitalization as an in-patient episode of recurrent ischemia or be performed during the re-hospitalization resulting from an out-patient episode of recurrent myocardial ischemia. In countries where waiting lists for revascularization procedures exist, revascularization within 30 days of an episode of recurrent ischemia will qualify as urgent. For patients with a previous PCI, it will be recorded if revascularization is necessary for previously treated vessels (i.e. urgent target vessel revascularization) and any occurrences of stent thrombosis will be documented. PCI is defined as any attempt at revascularization even if not successful (e.g. angioplasty, atherectomy, or stenting).
- Other definitions:
  - Recurrent cardiac ischemia: Cardiac ischemic symptoms  $>10$  minutes at rest (started with exercise or spontaneously and did not resolve with rest), resulting in hospitalization if an outpatient, or prolongation of hospitalization if an inpatient but not fulfilling criteria for MI.
  - Cardiac ischemic symptoms: chest pain or discomfort or equivalent (e.g. neck or jaw symptoms, dyspnea believed to represent an angina pectoris equivalent) believed due to impaired coronary flow secondary to atherosclerotic disease.

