### **Stent thrombosis**

Definite (presence of acute coronary syndrome with angiographic or autopsy evidence of thrombus or occlusion) or probable (unexplained deaths within 30 days after the procedure or acute myocardial infarction involving the target-vessel territory without angiographic confirmation).

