## 15.2 Sample Size and Power Considerations

### 15.2.1 Primary Endpoint

Sample size and power calculations for the study are based on the following assumptions:

- 2-sided log-rank test
- $\alpha = .05$
- Randomization ratio of 1:1

Data from the Mayo Rochester PCI registry demonstrate a 1 year rate of death, MI, or stroke of about 7.5% in PCIs from 2008-2009. Furthermore, the PLATO trial suggests we can expect stent thrombosis or severe, recurrent ischemia in about an additional 3%, resulting in a baseline rate of 10.5%. The rate is expected to be higher in \*2 or \*3 allele carriers who are discharged on clopidogrel, thus we assume a baseline rate of 12% for primary endpoint in the control arm.

Two studies suggest that the expected rate of 12% in Korean patients treated with clopidogrel after PCI for ACS. Kim et al. observed a 10.1% event rate for death, myocardial infarction, or stroke at 12 months in 306 patients with at least one *CYP2C19*\*2 or \*3 allele treated with PCI for acute myocardial infarction. As noted above, the PLATO trial suggests that stent thrombosis and severe recurrent ischemia may add 3% to this rate, which would result in a baseline rate over 12%. Oh et al. observed a 10.7% event rate for cardiac death, myocardial infarction and repeat revascularization at 12 months in 1011 patients treated with a drug-eluting stent (22% AMI, 78% stable) and carrying at least one *CYP2C19*\*2 allele. Assuming the event rate is higher in the

AMI subgroup and that the addition of stent thrombosis to the endpoint would increase the event rate, this study also suggests that a 12% event rate in the control group of Koreans may be expected.

Given that the vast majority of patients at the Mayo sites are of European heritage, we expect a reduced function allele prevalence of about 30% in those patients. The Canadian hospitals have a more diverse ethnic mix of patients, and we expect their prevalence to be anywhere from 30-50%. Thus, our sample size calculations assume an overall prevalence of reduced function allele carriers of 30% among patients recruited at those sites. We also assume the prevalence to be 50% in patients enrolled from South Korea and expect to enroll 1,015 subjects from there. Furthermore, we assume no more than 5% of patients will be lost to follow-up or drop out.

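### The spontaneous MI definition joins its two limbs with 'or', which contradicts the severe recurrent ischemia definition; this distorts component results, and no effect on the primary result is shown

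*Combined protocol and SAP*

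**What the plan says.** Section 12.3 introduces its list as binding on adjudication: "The following clinical event definitions will be used by the Adjudication Committee". Under Myocardial infarction, the spontaneous type is met when CK-MB or troponin is above the upper limit of normal by the hospital's "laboratory parameters or clinical presentation which is consistent or suggestive of ischemia". The connector between the two limbs is 'or'.

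Under Severe recurrent cardiac ischemia, the event is "Recurrent cardiac ischemia and at least one of the following, but not fulfilling the criteria for MI". The list that follows is new ischemic ECG changes or urgent revascularization. The base term is itself defined as ischemic symptoms at rest for more than 10 minutes that lead to, or prolong, a hospital stay, and that definition repeats the exclusion of MI.

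Two other MI rules in section 12.3 are conjunctive. For MI more than 24 hours after PCI, item (a) takes a biomarker rise and fall which, "together with at least one of the developments listed below, is a manifestation of myocardial infarction". Its last sub-item allows a documented diagnosis on the biomarker pattern "in the absence of any items enumerated in 1-4 due to conditions that may mask their appearance". The peri-CABG rule asks for biomarkers plus one further finding.

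Section 12.1 puts MI and severe recurrent ischemia in the same composite and adds "stent thrombosis if not captured in other events, from the time of randomization through one-year of follow-up". Section 15.2.1 starts from a registry rate of 7.5% for death, MI or stroke and expects "stent thrombosis or severe, recurrent ischemia in about an additional 3%, resulting in a baseline rate of 10.5" percent.

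**The concern.** A blinded committee can apply only the rule it is given. As written, the spontaneous MI rule absorbs the cases that severe recurrent ischemia is meant to hold, because the symptoms that define the second event already satisfy the second limb of the first. The two definitions cannot both work as intended.

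The individual components of the primary outcome are pre-specified exploratory outcomes (sections 2.3 and 12.2). A literal reading would inflate MI and nearly empty severe recurrent ischemia. Probable stent thrombosis includes "acute myocardial infarction involving the target-vessel territory without angiographic confirmation". If the committee uses its own MI definition there, the loose rule would also affect which cases carry that label.

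The 'or' also admits some events that a conjunctive rule would leave out of the composite altogether. Whether that touches the primary result depends on how many such events there are and how they respond to treatment.

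**Working it through.** **1. The plan's own sample size.** Inputs from section 15.2.1 and Table 3: control rate 12%, HR 0.65, two-sided alpha 0.05, power 80%, 1:1 allocation, 5% dropout.

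- Events: 4 × (1.960 + 0.842)² / (ln 0.65)² = 169.2
- Ticagrelor rate: 1 − (1 − 0.12)^0.65 = 7.97%
- Mean rate: (12% + 7.97%) / 2 = 9.99%
- Carriers: 169.2 / 0.0999 = 1,694.1 with unrounded inputs (stated 1,694)
- With dropout: 1,694 / 0.95 = 1,783.2, rounded up to 1,784 (stated 1,784)
- Rate build-up: 7.5% + 3% = 10.5%, which the plan then raises to 12% for carriers

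All figures reproduce. Only the total composite rate enters; the split between components does not.

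**2. The definitions side by side.** Let B be a biomarker above the local limit and P an ischemic presentation. Let R be ischemic symptoms at rest for more than 10 minutes with hospitalization or its prolongation, and F be new ischemic ECG changes or urgent revascularization. Any case with R also has P. The table applies outside the procedure-related MI windows.

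| Case | With 'or' | With 'and' | Composite changes? |
|---|---|---|---|
| B and P | MI | MI | No |
| P with R and F, not B | MI | Severe recurrent ischemia | No |
| B, not P | MI | Neither | Yes |
| P without both R and F, not B | MI | Neither | Yes |

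With 'or', every case that has R is already an MI, so severe recurrent ischemia has no members here. It is not strictly empty overall, because the periods after a non-index PCI or after CABG have their own MI criteria.

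**3. Relabelling (row 2).** The event counts on the same date under either label, and both labels belong to the composite. The 12% rate, the 1,694 carriers, the 80% power and the event time are therefore unchanged. The revised calculation in section 15.2.2 also uses only a total event rate. What changes is the split between MI and severe recurrent ischemia.

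**4. Extra events (rows 3 and 4).** These enter the composite only through the 'or', unless another component such as CV death already captures them. The documents give no count for either row. Row 3 is narrowed in practice: Table 1 collects biomarkers only from clinically indicated tests, and section 14.3 sends cases to adjudication when a MACE is suspected.

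**5. Direction of any effect on power.** Power is approximately Φ(√D × |ln HR| / 2 − 1.96), where D is the number of events. If the extra events do not respond to treatment, removing them lowers D but moves the HR further from 1. If they respond like the other events, removing them only lowers D and so lowers power. The documents do not say which applies.

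**6. Sign of use.** Section 15.2.2 reports 4.8% across all carriers, against the planned mean of 9.99% in step 1. That is no sign of over-counting, though it does not establish which rule was applied.

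**The case against.** The strongest reply is that the 'or' is a slip which an experienced committee would read correctly. The ischemia definition excludes MI twice, and both the later post-PCI rule and the peri-CABG rule ask for biomarkers plus something else. The separate 3% allowance also presumes events outside MI. This stands as evidence of intent, but it does not repair the text that the committee is told to use. The pattern is also not uniform. The rule for the first 24 hours after PCI rests on biomarkers alone at three times the limit, and item (b) of the later rule rests on imaging alone. No procedure-related rule, however, accepts symptoms alone.

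A second reply is that changing a primary component after event rates have been estimated is itself a risk. That is fair, and it is why the change should go no further than the contradiction requires.

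Three stronger readings might be inferred, and the documents support none of them:

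- *The 'or' costs the trial a definable amount of power.* Any such figure needs a share of extra events and their treatment response, and step 5 shows that even the sign depends on the latter.
- *The 3% allowance makes the sample size wrong.* It is a planning increment credited to an outside trial and added to a registry rate. The definitions behind both are not given, and the total does not depend on labels.
- *The rule biases against ticagrelor.* Dyspnea believed to be an angina equivalent counts as an ischemic symptom, and section 7.6.2 reports dyspnea in 13.8% on ticagrelor against 7.8% on clopidogrel. But adjudication is blinded, and nothing shows that such cases were called MI.

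**Conclusion.** The point holds as a contradiction between two endpoint definitions in section 12.3 that nothing in the documents resolves. Taken literally, the spontaneous MI rule nearly empties severe recurrent ischemia outside the procedure-related windows and distorts the exploratory component results.

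For the primary analysis, the relabelling effect is exactly zero on the composite, its timing, the sample size and the power. The remaining effect comes only from isolated biomarker rises, and from ischemic presentations that fail the rest, hospitalization, or ECG-or-urgent-revascularization requirements. Its size and direction cannot be determined from the documents.

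Confidence is high for the contradiction and low for any effect on the primary result. That a conjunctive rule was intended is an inference from neighbouring text. This is a wording correction to an endpoint definition; it gives no ground to question the sample size or the primary analysis.

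**What to change.** In the spontaneous MI definition, replace the 'or' between the biomarker limb and the clinical-presentation limb with 'and'. This reconciles it with the severe recurrent ischemia definition, which can stay as it is.

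Document the rule the Adjudication Committee has applied so far. If it already required both limbs, nothing further is needed. If the 'or' was used literally, re-review the affected calls, blinded to treatment and before database lock.

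The cost is a short amendment to the protocol or to the committee's instructions, plus a note of the rule applied; the re-review is conditional. The downside is possibly slightly fewer qualifying events.
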